7.2.5 Sponsor Responsibility for Reporting Adverse Events

All Adverse Events will be reported to regulatory authorities, IRB/IECs and investigators in accordance with all applicable global laws and regulations.

7.2.6 Investigator Responsibility for Reporting Adverse Events

It is the Case Comprehensive Cancer Center's Principal Investigator's responsibility to ensure that ALL serious adverse events are reported to the Case Comprehensive Cancer Center's Data Safety Toxicity Committee. This submission is simultaneous with their submission to the Sponsor or other Regulatory body.

8.0 STATISTICAL ANALYSIS PLAN

8.1 Study Design

This is a phase II trial evaluating the addition of concurrent and adjuvant fixed-dose pembrolizumab in combination with standard IMRT, in order to establish safety and estimate efficacy of this regimen to be tested in a subsequent randomized registration trial. At the conclusion of the study, the primary safety endpoint will be proportion of DLT. The primary efficacy endpoint will be 1-year PFS. Progression-free survival (PFS) will be calculated from treatment initiation to disease progression or death from any cause or last follow up.

8.2 Justification of Design and Sample Size:

The target sample size will be 34 patients. Assuming a <10% drop out or ineligibility rate, 37 patients will be enrolled to ensure 34 evaluable patients (all evaluable patients will be analyzed). The sample size was generated based on the primary safety endpoint. DLT $\leq 20\%$ is acceptable and $\geq 40\%$ is unacceptable. If 11 or more of 34 patients experience DLT, this regimen will be considered too toxic. The significance level and power of this design are 6% and 86%, respectively. If 8 or fewer patients experience DLTs, the regimen will be deemed safe to proceed for further study. If 9 or 10 patients experience DLTs, the PI will examine the type, reversibility and duration of DLTs and a careful decision will be made whether to pursue this regimen further in this adjuvant population.

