2.0 TRIAL DESIGN

2.1 Trial Design

- This is a phase II trial evaluating the addition of concurrent and adjuvant fixed-dose pembrolizumab in combination with standard IMRT, in order to establish safety and estimate efficacy of this regimen to be tested in a subsequent randomized registration trial. Thirty seven patients will be enrolled.
- The primary safety endpoint will be proportion of DLTs. The primary efficacy endpoint will be 1-year PFS. The primary signal to move forward with a subsequent confirmatory randomized study will be a $\leq 24\%$ overall DLT rate and a favorable 1yr PFS estimate compared to historical controls.

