4.2.3.2 Safety Endpoints

The primary safety endpoints for this study will be dose limiting toxicity (DLT). DLT for this study is defined as the occurrence of a severe adverse event (AE) listed below that is *at least possibly*

related to pembrolizumab, and occurs from the initiation of treatment thru 30 days after the final administration of the study treatment. AEs will be graded according to NCI CTCAE version 4.0. At the completion of the study, a total DLT rate will be assessed. A DLT rate of $\leq 24\%$ will be deemed acceptable and if met, the regimen will be deemed appropriate for future study in randomized studies.

The following events will be considered a DLT:

- Any \geq Grade 3 immune-related toxicity (including graft rejection), except:
 - Grade 3 dermatologic toxicity resolving to Grade 1 or lower with < 2 weeks of systemic immunosuppression
- Any \geq Grade 3 non hematologic toxicity **except**:
 - Grade 3 in-field radiation dermatitis for which IMRT is not held or held ≤ 1 week (5 fractions)
 - Grade 3 mucositis for which IMRT is not held or is held ≤ 1 week (5 fractions)
 - Asymptomatic Grade 3-4 hypomagnesemia or hypokalemia
 - Grade 3 fatigue
 - Grade 3 dysphagia or feeding tube use
 - Grade 3 weight loss
 - Grade 3 pain
- Grade 3 neutropenia with fever (oral temperature $> 39^{\circ}\text{C}$)
- Grade 3 thrombocytopenia with bleeding
- Grade 4 neutropenia with/without fever, requiring antibiotics
- Grade 4 thrombocytopenia
- Toxicity of any grade that results in inability to complete IMRT within 8 weeks

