8.3 Statistical Analysis Plan

DLT will be estimated using an exact 95% confidence interval. If 11 or more patients experience DLT the regimen will be considered too toxic. One-year PFS will be estimated using the Kaplan-Meier method and a 95% confidence interval constructed using Greenwood's method. One year PFS outcomes will be assessed overall and also separately for immunocompetent patients vs. immunosuppressed patients (e.g. CLL). These outcomes will be compared to our historical dataset for both subsets respectively. Adverse events will be tabulated by category and grade. The rates of

adverse events will be estimated using an exact 95% confidence. The relationship between 1yr PFS and baseline PD-L1 expression will be assessed using logistic regression. Immunoprofiles in peripheral blood in serial samples will be tested using random effects ANOVA. Bioinformatic analysis will be applied to all genomic and transcriptomic data.

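### The 6% and 86% in section 8.2 describe only the 11-of-34 toxicity boundary of a three-zone DLT rule, and the DLT go criterion differs between sections 2.1, 4.2.3.2, 5.4 and 8.2

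*Combined protocol and SAP*

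**What the plan says.** Section 8.2 sizes the trial on the primary safety endpoint. The planning values are "DLT $\leq 20\%$ is acceptable and $\geq 40\%$ is unacceptable", and "The target sample size will be 34 patients", with 37 enrolled to allow for losses. A count of 11 or more DLTs among 34 makes the regimen too toxic. The next sentence reads "The significance level and power of this design are 6% and 86%, respectively". Only after that does 8.2 bring in the other two zones. Eight or fewer is safe to take forward. For the middle zone, "If 9 or 10 patients experience DLTs, the PI will examine the type, reversibility and duration of DLTs", and a decision on whether to pursue the regimen follows. Section 8.3 repeats only the 11-or-more rule.

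Three other sections state a go criterion as a rate:

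- **2.1:** "The primary signal to move forward with a subsequent confirmatory randomized study will be a" DLT rate of 24% or less, together with a favorable 1-year PFS estimate against historical controls.
- **4.2.3.2:** a DLT rate of 24% or less "will be deemed acceptable and if met, the regimen will be deemed appropriate for future study in randomized studies".
- **5.4:** the same signal as 2.1, with the DLT rate set at 20% or less.

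**The concern.** The DLT endpoint is co-primary and is the only basis given for the sample size, so its error rates are the justification for 34 patients. A single pair credited to the design invites the reader to take 6% as the chance of losing an acceptable regimen and 86% as the chance of stopping an unacceptable one. That reading is right only if every count of 9 or 10 goes forward, which 8.2 does not say.

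The status of some counts also depends on the section read. Counts of 9 or 10 miss the 24% criterion in 2.1 and 4.2.3.2 but may be pursued under 8.2. Counts of 7 or 8 are a go under 8.2 and meet 24%, but miss the 20% in 5.4. If this is settled only once the count is known, the co-primary safety conclusion becomes a post hoc choice.

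**Working it through.** **Inputs.** From 8.2: n = 34 evaluable; acceptable DLT rate 20%; unacceptable rate 40%; cuts at 8 or fewer, 9 to 10, and 11 or more. From 2.1 and 4.2.3.2: 24% or less. From 5.4: 20% or less. The 30% row below is an added illustration midway between the two planning rates. X is the number of DLTs, taken as binomial(34, p).

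**Step 1: the plan's own figures.** P(X ≥ 11 | p = 0.20) = 0.0620 and P(X ≥ 11 | p = 0.40) = 0.8617. These round to the stated 6% and 86%. Neighbouring cuts do not give that pair:

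| Cut | P at true 20% | P at true 40% |
|---|---|---|
| 9 or more | 22.7% | 96.6% |
| 10 or more | 12.5% | 92.7% |
| **11 or more** | **6.2%** | **86.2%** |
| 12 or more | 2.7% | 76.7% |

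So the stated pair belongs to the 11-of-34 boundary alone.

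**Step 2: the three zones.** P(go) = P(X ≤ 8), P(review) = P(9 ≤ X ≤ 10), P(too toxic) = P(X ≥ 11).

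| True DLT rate | Go (8 or fewer) | PI review (9–10) | Too toxic (11 or more) |
|---|---|---|---|
| 20% | 77.3% | 16.5% | 6.2% |
| 30% | 26.8% | 28.7% | 44.6% |
| 40% | 3.4% | 10.4% | 86.2% |

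(The 30% row sums to 100.1% because of rounding.)

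**Step 3: what the review zone does to the error rates.**

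- True 20%, fails to go: 6.2% if every 9–10 result proceeds; 6.2% + 16.5% = 22.7% if none does.
- True 20%, goes: 77.3% if none proceeds; 77.3% + 16.5% = 93.8% if all do.
- True 40%, goes: 3.4% if none proceeds; 3.4% + 10.4% = 13.8% if all do.

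**Step 4: counts against the stated rates.** 6/34 = 17.6%, 7/34 = 20.6%, 8/34 = 23.5%, 9/34 = 26.5%, 10/34 = 29.4%.

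| Section | DLT criterion | Counts of 34 that meet it |
|---|---|---|
| 2.1, 4.2.3.2 | 24% or less | 8 or fewer |
| 5.4 | 20% or less | 6 or fewer |
| 8.2 | safe to proceed | 8 or fewer; 9–10 possible after review |

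Under 5.4, a regimen with a true 20% rate would miss the DLT criterion with probability P(X ≥ 7 | 0.20) = 53.4%.

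**The case against.** The strongest reply is that nothing is miscalculated. The 6%/86% sentence directly follows the 11-of-34 rule and comes before any mention of 8, 9 or 10, so a careful reader can attach it to that rule, and 8.3 repeats only that test. This stands: the figures are correct for that boundary, and it would be wrong to infer an arithmetic error. What remains is that the text credits the pair to the design as a whole, while the design has two further zones with no stated rates.

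A reader might also infer that the sections give flatly opposite answers at 9 or 10 DLTs. The documents do not go that far. Sections 2.1 and 4.2.3.2 set 24% as the criterion, and 4.2.3.2 says what follows if it is met; neither says that a higher rate must stop development. Section 8.2 does not call 9 or 10 a go either, but leaves a decision open. The conflict at 9–10 is by implication. The conflict between 24% and 20% for the same signal is explicit.

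A third tempting reading is that 22.7% and 96.6% are the error rates of the signal in 2.1. They are not, because that signal also requires a favorable 1-year PFS estimate. They apply to the DLT component alone.

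Finally, the review zone is a legitimate design choice, and its effect at a true 40% rate is bounded: even if every 9–10 result proceeds, the false-go rate is 13.8%, which is what 86% already implies. That also stands. The unreported cost falls on the other side, on acceptable regimens that do not get an automatic go.

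One might add that the planned interval ("DLT will be estimated using an exact 95% confidence interval") runs from 10.7% to 41.2% at 8/34 and so includes 40%. This contradicts nothing: the interval is for estimation and the decision rests on a count.

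**Conclusion.** The concern holds as a matter of consistency and reporting. The stated pair describes one boundary of a three-zone rule. The chance that a regimen with a true 20% rate gets an automatic go is 77.3%, not the 93.8% that a 6% error rate implies, and the unspecified handling of 9–10 leaves its failure-to-go rate anywhere from 6.2% to 22.7%. At a true 40% rate the go-forward probability lies between 3.4% and 13.8%. Separately, three different DLT go criteria are in force, and they disagree or are unclear for counts of 7 through 10.

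These figures assume exactly 34 evaluable patients and independent DLTs with a common rate. They concern the DLT component only.

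**What to change.** 1. In 8.2, state that 6% and 86% are the probabilities of crossing the 11-of-34 too-toxic boundary at true rates of 20% and 40%, and add the three-zone table.
2. Reconcile 2.1, 4.2.3.2, 5.4 and 8.2 to one DLT go criterion.
3. State, before the DLT count is known, whether 9 or 10 of 34 can meet the DLT component of the signal. Quote the matching error rates, labelled as those of the DLT component only: with 24% or less and 9–10 not meeting it, 22.7% failure to go at a true 20% rate and 3.4% go at 40%; with 9–10 all proceeding, 6.2% and 13.8%. If the outcome is left to PI review, give the ranges.

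The PI review can stay. The sponsor may keep it and amend the other sections, or narrow it; what is needed is that the sections agree. No extra confidence bound is required.

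The cost is wording only, with no change to sample size or data collection. The downside is a less favourable stated figure: a 77% chance of an automatic go for an acceptable (20%) regimen instead of the implied 94%.

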8.3 Statistical Analysis Plan

DLT will be estimated using an exact 95% confidence interval. If 11 or more patients experience DLT the regimen will be considered too toxic. One-year PFS will be estimated using the Kaplan-Meier method and a 95% confidence interval constructed using Greenwood's method. One year PFS outcomes will be assessed overall and also separately for immunocompetent patients vs. immunosuppressed patients (e.g. CLL). These outcomes will be compared to our historical dataset for both subsets respectively. Adverse events will be tabulated by category and grade. The rates of

adverse events will be estimated using an exact 95% confidence. The relationship between 1yr PFS and baseline PD-L1 expression will be assessed using logistic regression. Immunoprofiles in peripheral blood in serial samples will be tested using random effects ANOVA. Bioinformatic analysis will be applied to all genomic and transcriptomic data.

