4.2.3.3 Rationale for Correlative Endpoints/Biomarker Research

Central hypothesis: Cutaneous squamous cell carcinoma (CSCC) is responsive to combination of PD-1 inhibition and radiation therapy.

To test our hypothesis correlatively we propose the following aims:

Aim 1. To correlate baseline PD-1 expression in the tumor with disease related outcomes.

Rationale: It is unknown whether patients with tumors that express higher levels of PD-1 preferentially respond compared to those that do not. As such, this will be systematically evaluated on all patients.

Research Plan: FFPE tissue blocks will be collected from patients and slides will be cut for subsequent biomarker staining. Analysis of PD-L1 expression will be performed by immunohistochemical staining using the Merck assay. Either complete circumferential or partial linear plasma membrane staining will constitute positive PD-L1 staining. A cut-off of $\geq 5\%$ tumor cell membrane staining will be reported as positive.

Aim 2. To define response to radiation/PD-1 inhibition based on tumor microenvironment and peripheral blood alterations in patients with CSCC.

Rationale: Many solid tumors do respond to checkpoint inhibitors. Little is known in regards to CSCC patients who will or will not respond to the proposed treatment regimen of post-operative radiation and anti-PD-1 therapy.

Research Plan: Prospectively we will stratify study patients into two groups: those that do, or do not respond to the proposed therapy based on historical published data from our institution. The following are the proposed assays for evaluation.

A. Peripheral Blood Lymphocytes

Flow cytometry: Peripheral blood samples drawn from patients pretreatment and at specified times post treatment will be isolated by centrifugation. Surface biomarker expression will be assessed by FACS similar to the analysis of tumor-resident lymphocytes. Staining will evaluate CD3, CD4, CD8 expression as well as cytotoxic markers (perforin, FasL, Granzyme A&B, markers of dysfunction/exhaustion (PD-1, TIM-3, Lag-3), and markers characteristic of regulatory cells (Foxp3, CD25, GITR, CD27, CD28) and markers for myeloid derived suppressor cells. Finally, we will assess TCR clonal diversity using PCR methods.

B. Tissue

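### If PD-L1 enters the logistic model as positive/negative, an empty cell in about 34 patients would leave no finite odds ratio and a Wald p-value near 1, and section 8.3 names no method that copes

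*Combined protocol and SAP*

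**What the plan says.** Section 8.3 states: "The relationship between 1yr PFS and baseline PD-L1 expression will be assessed using logistic regression". It does not say how PD-L1 is coded, which test is used, or what is done if the model has no finite solution.

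Section 4.2.3.3 (Aim 1) sets the reporting rule for the stain: "A cut-off of $\geq 5\%$ tumor cell membrane staining will be reported as positive". A positive/negative term is therefore the likely reading of 8.3, though 8.3 does not itself say so.

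Section 8.2 fixes the number of patients: "The target sample size will be 34 patients", with 37 enrolled. That number was derived from the DLT endpoint alone. No effect size, significance level or power is attached to the PD-L1 analysis.

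Section 3.2 lists as a hypothesis that PD-L1 at baseline has no bearing on 1-year PFS. Section 4.2.3.1 calls 1-year PFS in this population suboptimal but gives no figure, and no section gives the expected share of PD-L1 positive patients.

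**The concern.** Logistic regression without further qualification means maximum likelihood. With one binary predictor, the fitted odds ratio is the cross-product ratio of the two-by-two table. If one PD-L1 group has no events, or only events, that ratio is zero or infinite. Software then stops at an arbitrary large coefficient with an enormous standard error, and their ratio, the Wald statistic, is close to zero. The printed p-value is near 1 whether the imbalance is trivial or extreme.

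What makes this more than a nuisance is the direction of the stated hypothesis. The protocol expects no association. A p-value near 1 from a fit that failed looks the same as one from a fit that found nothing, so a strong association could be written up as confirming the hypothesis.

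**Working it through.** **1. The plan's own sizing.** The only sizing figures in the documents belong to the DLT rule. For "If 11 or more of 34 patients experience DLT, this regimen will be considered too toxic", exact binomial tails give P(X ≥ 11 | n = 34, 20%) = 0.062 and P(X ≥ 11 | n = 34, 40%) = 0.862, matching "The significance level and power of this design are 6% and 86%, respectively". Going from 37 to 34 loses 3/37 = 8.1%, consistent with the stated limit of under 10%. So n = 34 is sound for DLT, but says nothing about PD-L1.

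**2. Chance of an empty cell.**

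Inputs: n = 34 (section 8.2). PD-L1 prevalence and 1-year PFS are assumptions, because the documents give neither.

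Let k be the number of PD-L1 positive patients, distributed Binomial(34, prevalence), and let s1 and s0 be 1-year PFS in positives and negatives. Given k:

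- a = s1^k + (1 − s1)^k, the chance that the positive group has no events or only events
- b = s0^(34−k) + (1 − s0)^(34−k), the same for the negative group
- P(empty cell) = a + b − ab

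For example, with k = 17 and PFS 75% in both groups, a = b = 0.75^17 + 0.25^17 = 0.0075, and P = 0.015. Averaging over k at 50% prevalence gives 2.1%. Tables with all patients in one PD-L1 group count as not estimable.

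| 1-year PFS (positive / negative) | 20% positive | 30% | 40% | 50% |
|---|---|---|---|---|
| 60% / 60% | 7.1% | 1.4% | 0.3% | 0.1% |
| 75% / 75% | 17.9% | 7.2% | 3.2% | 2.1% |
| 85% / 85% | 36.5% | 22.8% | 15.9% | 13.7% |
| 90% / 90% | 53.5% | 41.2% | 34.4% | 32.2% |
| 90% / 75% | 50.4% | 35.6% | 25.3% | 18.4% |

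**3. What the methods report on particular tables** (events in positives against negatives, 34 patients).

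*0/17 against 8/17.*
- Wald: coefficient −22.45, SE 11,689; the ratio is −0.002, p 0.9985.
- Likelihood ratio, from the same fit: log-likelihood with PD-L1 is 8 ln(8/17) + 9 ln(9/17) = −11.754; without it, 8 ln(8/34) + 26 ln(26/34) = −18.550. Twice the difference is 13.59, p 0.0002.
- Fisher: p 0.0027.
- Firth: for one binary predictor the estimate equals adding one half to each cell, so the odds ratio is (0.5 × 9.5)/(17.5 × 8.5) = 0.032. The penalized likelihood-ratio p is 0.0009, and the profile 95% interval is about 0.0002 to 0.3.

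*0/10 against 5/24.*
- Wald p 0.9989; likelihood-ratio p 0.050; Fisher p 0.29.
- Firth odds ratio (0.5 × 19.5)/(10.5 × 5.5) = 0.169, p 0.15. The interval includes 1.

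*1/17 against 8/17.* One event in the cell is enough to restore the Wald test: p 0.020, with Fisher p 0.017 and Firth p 0.007.

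**4. How many empty-cell tables hide a signal.** Over the same enumeration, count tables with an empty cell and a Firth p below 0.05. With PFS 90% against 75%, this is 7.4%, 9.9% and 9.4% at 30%, 40% and 50% positive, out of the 35.6%, 25.3% and 18.4% above. With no association and PFS of 75-90%, it is about 1-2%.

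**The case against.** Four points on the other side deserve weight.

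- **Frequency.** A reader might infer that the model will often fail. The documents do not support that. It depends on two figures they do not give, and what they do say points away from very few events: section 4.2.3.1 calls 1-year PFS suboptimal, and section 4.2.1 speaks of considerable failure rates. At PFS 60% with 30-50% positive, the chance is 1.4% or less. This stands: the claim can only be that an empty cell may occur.
- **The test.** A reader might infer that the plan commits to a Wald p-value. It names no test. A likelihood-ratio p from the ordinary fit stays usable (0.0002 in the 0/17 table). This stands for the p-value, but not for the estimate, which that test leaves without a finite value.
- **The coding.** The 5% rule governs how the stain is reported, and Aim 1 also speaks of higher levels of expression. A continuous staining percentage forms no two-by-two cell, and separation would then be a different and usually rarer event. This stands, and is why the coding must be stated.
- **The harm.** A reader might infer that every empty cell buries a real finding. It does not: 0/10 against 5/24 is not significant under Firth, and with PFS 90% against 75% about half or more of the empty-cell tables are not.

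None of this supplies a fallback, and a method chosen after the table has been seen is open to challenge.

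**Conclusion.** The point holds as a conditional one. If PD-L1 is analysed as positive/negative and a cell is empty, maximum likelihood gives no finite odds ratio, and a Wald p-value would be near 1 regardless of the data. At n = 34 the chance ranges from about 0.1% (PFS 60%, half positive, no association) to 41% (PFS 90%, 30% positive, no association). It is higher still if one PD-L1 group holds 20% of patients or fewer. It becomes common only with PFS of about 85% or more, a small PD-L1 group, or one group that does very well. Missing tissue or censoring before one year would reduce n and raise these figures somewhat.

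The consequence is limited. PD-L1 is a correlative objective, no go-forward decision in section 2.1 depends on it, and the primary DLT and PFS conclusions are untouched. The specific risk is that a failed fit is read as support for the hypothesis of no association. This is a minor but cheap improvement.

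**What to change.** In section 8.3, state that PD-L1 enters the model as positive/negative at the 5% cut-off of section 4.2.3.3. State also that the logistic model will be fitted by Firth penalized likelihood, reporting the odds ratio with a profile-likelihood confidence interval and a penalized likelihood-ratio p-value.

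The cost is one sentence and standard software. The downside is slight shrinkage toward no effect: in the 1/17 against 8/17 table the ordinary odds ratio is (1 × 9)/(16 × 8) = 0.07 and the Firth value is 0.10. A likelihood-ratio or Fisher test would also give a usable p-value, but Firth supplies a finite estimate and interval as well.
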